## **6.2 Exclusion Criteria**

Subjects will be excluded from the study if they have:

1. History of or active central nervous system (CNS) malignancy
2. Allogeneic stem cell transplant within the last 6 months, or active graft versus host disease following allogeneic transplant, or subjects currently on immunosuppressive therapy following allogeneic transplant.
3. Uncontrolled intercurrent illness including, but not limited to, ongoing active infection, symptomatic congestive heart failure, unstable angina pectoris, cardiac arrhythmia, or psychiatric illness/social situation that would limit compliance with study requirements as judged by treating physician; subjects receiving antibiotics that are under control may be included in the study
4. Pregnant or breastfeeding women.
5. Clinically symptomatic and uncontrolled cardiovascular disease

6. History of myocardial infarction, severe/unstable angina, or symptomatic congestive heart failure, within the 6 months prior to study drug administration
7. Current or recent history (< 21 days prior to start of treatment) of a clinically significant bacterial, viral, fungal, parasitic or mycobacterial infection.
8. History of other malignancy, with the exception of squamous cell carcinoma of the skin, basal cell carcinoma of the skin, cervical intraepithelial neoplasia, or other malignancies that have been in remission for at least 3 years
9. Presence of a malabsorption syndrome possibly affecting drug absorption (eg, Crohn's disease or chronic pancreatitis).
10. Any prior or concomitant use of another JAK inhibitor.
11. Known active hepatitis B or C, or HIV infection.
12. Subjects who, in the opinion of the Investigator, are unable or unlikely to comply with the dosing schedule and study evaluations.

## 7.0 SCHEDULE OF OBSERVATIONS

### 7.1 Schedule of Observations Flowchart

	Screening		Cycle 1 (+/- 2 days each time point)				Cycle 2	Every Cycle thereafter	End of Treatment	Follow-up
	$\leq 28$ days	$\leq 14$ days	Day 1	Day 8	Day 15	Day 22	Day 1 (+/- 7 days)	Day 1 (+/- 7 days)	(+/- 7 days)	(each time point +/- 4 weeks)
Evaluation										
Informed consent	X									
Medical history	X									
Physical examination		X					X	X	X	
Vital Signs		X					X	X		
ECOG performance score		X					X	X		
Concomitant medications		X	X				X	X	X	
12-lead ECG		X a								
Serum Pregnancy test		X a								
Hematology Lab		X	X b	X	X	X	X	X	X	
Chemistry Lab		X	X b	X	X	X	X	X	X	
PET scan		X c								
CT scan		X c						X c	X c	
Bone Marrow Biopsy								(X) d		
Tumor Tissue collection for GEP,IHC or other subtype analysis		X e						(X) e	(X) e	
Archive Tissue collection		X								
Blood Sampling for Cytokine Profiling f			X b,f	X f	X f	X f	X			
Blood Sampling for CRPg			X				X		X	
Study med dispensed			X				X	X		
Adverse event reporting	X		X	X	X	X	X	X	X h	
Compliance assessment – study med.			X	X	X		X	X	X	
Subject Status										X i

- a. Repeat ECG's and pregnancy testing are not required but may be repeated throughout the study at the discretion of the investigator.
- b. Cycle 1, day 1 Hematology and Chemistry labwork may be collected within 7 days prior to C1, D1 study drug dosing.
- c. Baseline staging should include measurable disease by CT scan and a PET scan. If sites can accomplish tumor measurements with one PET/CT scan, this will be acceptable. CT scans will be done for restaging purposes. In subjects with cutaneous lesions only, bidimensional measurements and photographs will be used for response assessment. PET scan may be repeated to confirm PR or CR at the discretion of the investigator. Disease restaging will occur after 2 cycles concurrent with the start of Cycle 3 and then every 2 cycles thereafter. In subjects who are beyond the post cycle 6 response assessment AND have demonstrated objective response (PR or CR) restaging may be done every 3 cycles thereafter.
- d. Bone marrow aspirate and biopsy will be performed to confirm complete remission unless the subject had a documented negative bone marrow biopsy evaluated with 45 days prior to treatment initiation.
- e. Tumor excisional biopsy or 2 core biopsies are required at baseline and are optional during treatment at time of disease progression (post Cycle 2) and End of treatment. See appendix 2 for tumor tissue collection, processing and shipping instructions.
- f. The Cycle 1, day 1 blood may be collected within 7 days prior to initiation of ruxolitinib. On Cycle 1, Day 1 only, an additional blood for cytokine analysis will be drawn 3 hours after the first dose of ruxolitinib. See appendix 2 for cytokine collection, processing and shipping instructions. Blood for cytokine analysis will be drawn prior to the morning dose of ruxolitinib on days 8, 15, 22 in Cycle 1 and on Cycle 2, day 1.
- g. Blood for C-reactive protein (CRP) will be analyzed from blood collected for cytokine profiling at pre-treatment (within 7 days prior to initiation of ruxolitinib) and at cycle 2, day 1. An additional blood sample for CRP will be collected at time of progression or relapse.
- h. All subjects must be followed for safety for at least 30 days after study treatment has ended, or until study drug related toxicities resolve, return to Baseline or are deemed irreversible, whichever is longer.
- i. Subjects will be followed every 3 months for the first year and every 6 months thereafter via clinic contact or telephone to obtain disease status and survival information (see section 7.6).

## **7.2 Screening Evaluations and Subject Enrollment**

**7.2.1** The following procedures will be performed at the Screening visit within 28 days prior to start of treatment unless noted otherwise:

- Informed consent must be obtained before study-specific screening evaluations are performed, unless performed as standard of care. The informed consent process should be documented in the subject's medical chart.
- Medical history;
- Physical examination, including height, weight, and clinical signs and symptoms (within 14 days prior to cycle 1 day 1);
- Vital signs, including pulse, systolic and diastolic blood pressure (BP), respiration rate, and body temperature (within 14 days prior to cycle 1 day 1);
- ECOG performance status (within 14 days prior to cycle 1 day 1);
- Single 12-lead ECG;
- Hematology: CBC with differential within 14 days prior to cycle 1 day 1 (see section 8.2.5);
- Blood chemistry within 14 days prior to cycle 1 day 1 (see section 8.2.5);
- Serum pregnancy test for women of child-bearing potential (within 14 days prior to cycle 1 day 1);
- Concomitant medications (within 14 days prior to cycle 1 day 1);
- Whole body PET scan and CT of chest, abdomen and pelvis (may include neck at the discretion of the investigator).
- Tumor tissue collection must be obtained on all subjects prior to start of treatment (see section 5.2.1 and appendix 2 for details) for research evaluation.
- Archived tumor tissue from time of initial diagnosis of DLBC or PTCL must be obtained for research evaluation and correlation with the current tissue sample.

### **7.2.2 Subject Enrollment**

The results from the Screening visit evaluations will be reviewed to determine if the subject continues to meet the eligibility requirements as specified in the protocol. If a subject does not meet eligibility requirements or withdraws consent prior to treatment initiation, then that subject will be determined a screen failure and will not be eligible to receive treatment in the study.

Subjects who have signed the informed consent and meet all the entry criteria (see Inclusion/Exclusion Criteria) will be enrolled in the study. At the time of enrollment a subject study identifier will be assigned by the sponsor.

### **7.3 On-Treatment Evaluations**

Cycle 1, Day 1 Assessments:

- Hematology and Chemistry laboratory assessments unless completed within 7 days prior (see section 8.2.5) to treatment. If the screening laboratory assessments were collected within 7 days prior to treatment, these results may be also used for the Cycle 1, day 1 assessment.
- Vital Signs within 30 minutes prior to first dose
- AE assessment
- Con Meds
- Subjects will be prescribed ruxolitinib orally twice daily. A cycle consists of 28 consecutive days of BID dosing. (See section 9.0)
- Blood Samples for Cytokine Profiling and C reactive protein analysis will be collected within 7 days before first dose and blood for cytokine profiling will be collected at 3 hours after the first dose of ruxolitinib. (see appendix 2)
- Vital Signs one hour after first dose.
- Subjects will be instructed to take doses approximately 12 hours apart.
- Subjects will be asked to complete a study drug dosing diary and to return all empty study drug bottles and completed diaries to the study center.

Cycle 1, weekly assessments on Day 1, Day 8, Day 15, and Day 22:

- Hematology and chemistry laboratory assessments (see section 8.2.5)
- Blood Sample for Cytokine Profiling will be collected prior to the morning dose of ruxolitinib (see appendix 2)

Cycle 2, and each subsequent Cycle assessments:

- Hematology and Chemistry laboratory assessments (see section 8.2.5)

- Cycle 2, Day 1 only: Blood Sample for Cytokine Profiling and C-reactive protein analysis will be collected prior to initiation of cycle 2 dosing (see appendix 2).
- Vital Signs
- AE assessment
- Concomitant Medications
- Physical Exam
- ECOG performance status
- Optional fresh tumor sample collection: Either excisional biopsy or two 14 gauge or larger,  $\geq$  2cm length cores will be obtained sometime after the completion of 2 cycles of treatment (see appendix 2).

Disease restaging will occur after 2 cycles concurrent with the start of Cycle 3 and then every 2 cycles thereafter. In subjects who are beyond the post cycle 6 response assessment AND have demonstrated objective response (PR or CR) restaging may be done every 3 cycles thereafter. The following tests will be completed:

- CT scan chest, abdomen, pelvis. However, in subjects with measurable cutaneous lesions only, photographs and bidimensional measurements of skin lesions may be utilized for response assessment. The Investigator should take care to ensure consistency in response assessment evaluation throughout the study.
- PET scan may be performed at the discretion of the investigator to confirm CR or PR
- If subject has complete remission by CT or CT/PET scan perform a bone marrow biopsy for confirmation of complete response unless the patient had a documented negative bone marrow biopsy within 45 days prior to treatment initiation.

#### **7.4 Duration of Participation**

Subjects who are demonstrating benefit may continue to receive treatment with ruxolitinib unless a criterion for discontinuation from the study has been met. The criteria for study discontinuation are listed below:

- unacceptable toxicity;
- disease progression or relapse
- investigator discretion
- withdrawal of consent
- pregnancy

If a subject is withdrawn from the study treatment for any reason, the study sponsor-investigator must be notified and an end-of-treatment visit should be performed. Follow-up evaluations will also be performed in accordance with the protocol requirements.

## **7.5 End-of-treatment Evaluations**

Subjects who are withdrawn from the study treatment for any reason will have evaluations performed at End-of-Treatment. The following evaluations and procedures will be performed at this visit.

- AE assessment
- Concomitant Medications
- Physical Exam
- ECOG performance status
- Hematology and Chemistry laboratory assessments
- Documentation of response
- All subjects must be followed for safety for at least 30 days after ruxolitinib treatment has ended, or ruxolitinib related toxicities resolve or return to Baseline or are deemed irreversible, whichever is the longer duration.
- At time of relapse subjects will have a blood sample collected for C-reactive protein evaluation (see appendix 2. II. C)
- Optional fresh tumor sample collection: subjects who have documented disease progression will have either excisional biopsy or two 14 gauge or larger,  $\geq 2\text{cm}$  length cores within 6 weeks post treatment (see appendix 2).

## **7.6 Follow-up Evaluations**

Subjects will be followed every 3 months for the first year and every 6 months thereafter via a clinic visit or contact by telephone by research staff personnel to obtain the following information:

- Disease Status will be collected until first documented relapse or progression of the disease under study;
- Date last alive or date of death

## **8.0 STUDY ASSESSMENTS**

### **8.1 Demographic and Other Pre-Treatment Assessments**

After written informed consent is obtained, demographic data and a complete medical and medication history will be collected at Screening. Height, body weight and BMI measurements will be done. Medical history will be updated up through the first dose of study medication, after which adverse events will be recorded. Disease staging, laboratory assessments, physical exam, performance status will be completed as outlined in the study flowchart. In addition, all subjects will undergo tumor biopsy for exploratory tumor GEP and IHC studies.

### **8.2 Safety Assessments**

#### **8.2.1 Adverse Events**

Adverse events will be monitored continuously during the study after the first dose of study medication. Subjects will be instructed to report all AEs during the study and subjects will be assessed for the occurrence of AEs throughout the study. All AEs (serious and nonserious) must be recorded on the source documents and case report forms regardless of the assumption of a causal relationship with the study medication. The definition, reporting, and recording requirements for AEs are described in Section 11.

#### **8.2.2 Physical Examinations**

A comprehensive physical examination will be performed at the times indicated on the Schedule of Observations. The comprehensive physical examination will include the following organ or body system assessments: skin; head, eyes, ears, nose, and throat; thyroid; lungs; cardiovascular; abdomen (liver, spleen); extremities, lymph nodes, and a brief neurological exam.

#### **8.2.3 Vital Signs**

Vital sign measurements (blood pressure, heart rate, and body temperature) will be collected on the days and times noted in the Schedule of Observations.

#### 8.2.4 12-Lead ECG Interpretation

The baseline 12-lead ECG will be interpreted by the Investigator at the site and will be used for immediate subject management. Subsequent ECG evaluations may be performed at the discretion of the investigator. The decision to include/exclude a subject or discontinue a subject's participation in the study based on an ECG flagged as "Abnormal, Clinically Significant" is the responsibility of the Investigator.

#### 8.2.5 Clinical Safety Laboratory Assessments

All subjects will have samples of blood collected on the days and times noted in the Schedule of Observations for analysis of serum chemistry, hematology, and pregnancy status. The hematology panel will include: hematocrit, hemoglobin, platelet count, red blood cell count, white blood cell count, absolute basophils, absolute eosinophils, absolute lymphocytes, absolute monocytes, absolute neutrophils, blasts. The chemistry panel will include: sodium, potassium, calcium, blood urea nitrogen (BUN), creatinine, total (unconjugated) bilirubin, glucose, total protein, albumin, alanine aminotransferase (ALT), aspartate aminotransferase (AST), lactic dehydrogenase (LDH), alkaline phosphate.

## 9.0 TREATMENT OF SUBJECTS

### 9.1 Investigational Product(s) Description

#### 9.1.1 Dosage and Dose Regimen

Open label ruxolitinib will be supplied by Incyte Corporation. Ruxolitinib tablets (5 mg) will be administered as oral doses without regard to food in an outpatient setting. Starting doses will be either 15 mg BID or 10 mg BID as described in Section 9.2. Maximum dose will not exceed 25 mg BID. A cycle consists of 28 consecutive days of BID dosing. Dosing is continuous without planned interruptions between cycles. Dosing may be interrupted or modified due to toxicities (see section 9.2).

#### 9.1.2 Packaging and Labeling

Ruxolitinib 5 mg tablets are packaged as 60-count in high-density polyethylene (HDPE) bottles. The bottles will include labeling “New Drug - Limited by Federal (USA) Law to Investigational Use”.

#### 9.1.3 Storage/Stability

The bottles of tablets should be stored at room temperature, 15°C to 30°C (59°F to 86°F). Stability studies will be conducted on all clinical batches to support the clinical trial.

#### 9.1.4 Drug Accountability

Responsibility for drug accountability at the study site rests with the Investigator; however, the Investigator may assign some of the drug accountability duties to an appropriate pharmacist or designee. Inventory and accountability records must be maintained and readily available for inspection by the study monitor and are open to inspection at any time by any applicable regulatory authorities.

The Investigator or designee will be expected to collect and retain all used, unused, and partially used containers of study medication until the end of the study. The Investigator or designee must maintain records that document:

- investigational product delivery to the study site
- the inventory at the site
- use by each subject including pill/unit counts from each supply dispensed
- product returned to the Investigator or designee.

These records should include dates, quantities, batch/serial numbers (if available), and the unique code numbers (if available) assigned to the investigational product and study subjects.

The investigational product must be used only in accordance with the protocol. The Investigator will also maintain records adequately documenting that the subjects were provided the study medication specified.

Completed accountability records will be archived by the site. If any unused ruxolitinib bottles remain at the end of the study, they will be accounted for at the site close-out visit. If a site is able to destroy ruxolitinib at their premises, or through a certified vendor, they may do so upon authorization by the Sponsor, provided their destruction policy is made available to the Sponsor.

## **9.2 Administration of Study Medication**

### **9.2.1 Starting Dose Assignment**

Continuous BID dosing is planned. A cycle is 28 days of BID dosing. The starting dose of ruxolitinib tablets will be determined based on Baseline platelet count as follows:

- Subjects with Baseline platelet count  $\geq 100,000/\mu\text{L}$  will begin dosing at 15 mg BID (three 5 mg tablets BID).
- Subjects with Baseline platelet count of 75,000/ $\mu\text{L}$  to  $<100,000/\mu\text{L}$  will begin dosing at 10 mg BID (two 5 mg tablets BID).

A standardized dosing paradigm will be used to determine dose adjustments for safety and efficacy so that each subject is titrated to their most appropriate dose. Doses will not exceed 25 mg BID.

### **9.2.2 Dose Increases**

The initial dose of ruxolitinib will be determined by the Baseline platelet count value. After every 2 cycles (post cycle 2, 4, 6, etc.) of therapy, at the discretion of the

investigator, the dose may be increased in 5 mg BID increments, to a maximum dose of 25 mg BID for subjects who meet all three of the following conditions:

1. Inadequate efficacy is demonstrated by no response or stable disease relative to baseline.
2. Platelet count is  $\geq 50,000/\mu\text{L}$  and platelet count has never been below  $50,000/\mu\text{L}$  at a prior laboratory evaluation since Baseline.
3. Absolute neutrophil count levels have remained at or above  $1000/\mu\text{L}$  since baseline.
4. No grade 4 anemia has been observed since baseline.

#### 9.2.3 Dose Adjustments for Safety

Dosing must be held for toxicities according to Table 1. In order to provide sufficient data to make the dose adjustment decisions, it is recommended that hematology parameters be obtained at least weekly for platelet count  $< 50,000/\mu\text{L}$  or ANC  $< 1000/\mu\text{L}$  and at least two times weekly for platelet count  $< 25,000/\mu\text{L}$  or ANC  $< 500/\mu\text{L}$ . Dosing may be restarted or increased following recovery of toxicities to acceptable levels. Subjects with hematologic toxicities requiring dose holds for 3 weeks or longer will be removed from the study.

The objective for restarting or escalating after a reduction for safety is to find the highest safe dose of ruxolitinib for each subject, with increases in dose not more than in increments of 5 mg BID and not more often than every 2 cycles.

**Table 1 Dose Modification Guidelines**

NCI CTCAE Toxicity Grade	Action Required
Thrombocytopenia: Platelets < 35,000 /uL	

• Hold (interrupt dosing)

• Follow CBC at least twice weekly

• If thrombocytopenia resolved to < Grade 2 (50,000/uL, may restart at next lower dose level)

• Subjects in whom benefit is seen and who recover to at least 40,000/uL platelets, may be considered for retreatment with a dose reduction after consultation with the study PI on a case by case basis.

Grade 3 or 4 Neutropenia (ANC <1000/uL)	

• Hold (interrupt dosing)

• Follow CBC at least weekly

• If neutropenia resolves to <math>\leq</math> Grade 2, may restart at next lower dose level

• Use of growth factors is permitted at the discretion of the investigator

• Subjects in whom benefit is seen and who recover to at least grade 3 ANC, may be considered for retreatment with a dose reduction after consultation with the study PI on a case by case basis.

Grade 4 Anemia (life-threatening, urgent intervention indicated)	

• Hold (interrupt dosing)

• Follow CBC at least weekly

• If anemia resolves to <math>\leq</math> Grade 2, may restart at next lower dose level

• Use of transfusions and/or erythropoietin is permitted at the discretion of the investigator

Related Grade 3 non-hematologic Toxicities	

• Hold (interrupt dosing)

• Manage toxicity according to institutional guidelines

• If toxicity resolves to <math>\leq</math> Grade 2 within 2 weeks, the subject may restart at next lower dose level or maintain per the investigator discretion

Related Grade 4 non-hematologic toxicities	

• Discontinue dosing

• Remove subject from the study

**NOTE: Whether the dose interruption occurred because of neutropenia, thrombocytopenia, anemia or any combination of cytopenias, all cytopenias must be considered to determine the ‘new’ dose that the subject will receive. The lowest calculated dose will be used and in all cases the maximum dose must not exceed 5 mg BID LESS than the dose that resulted in the toxicity that required the dose interruption. Subjects with hematologic toxicities requiring dose holds for 3 weeks or longer will be removed from the study, unless permission is granted from the study PI on a case by case basis.**

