**Table 2 Optional Dose Increase or Mandatory Reduction Levels for Subjects initiating treatment at 15 mg daily**

+2 Dose Level	25 mg BID daily for 28 days per cycle
+1 Dose Level	20 mg BID daily for 28 days per cycle
Starting Dose	15 mg BID daily for 28 days per cycle
-1 Dose Level	10 mg BID daily for 28 days per cycle
-2 Dose Level	5 mg BID daily for 28 days per cycle

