**Table 3 Optional Dose Increase or Mandatory Reduction Levels for Subjects initiating treatment at 10 mg daily**

+3 Dose Level	25 mg BID daily for 28 days per cycle
+2 Dose Level	20 mg BID daily for 28 days per cycle
+1 Dose Level	15 mg BID daily for 28 days per cycle
Starting Dose	10 mg BID daily for 28 days per cycle
-1 Dose Level	5 mg BID daily for 28 days per cycle

In summary, it is the intention to identify the optimal dose for each individual subject over the first several weeks of therapy as follows:

- Starting dose determined by baseline platelet count level.
- Optional dose increase after every 2 cycles if an objective response (PR or CR) was not achieved and no significant thrombocytopenia or neutropenia was observed.
- Frequent monitoring of hematology parameters, with mandatory dose decreases for toxicities.

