## **APPENDIX 3 – GRADING OF ADVERSE EVENTS**

Adverse Events will be graded according to the National Cancer Institute Common Toxicity Criteria for Adverse Events (CTCAE), Version 4, which may be found at the following website:

[http://ctep.cancer.gov/protocolDevelopment/electronic\\_applications/ctc.htm#ctc\\_40](http://ctep.cancer.gov/protocolDevelopment/electronic_applications/ctc.htm#ctc_40)

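### In Table 1 the platelet restart criterion gives a grade and a number that appear not to match, leaving counts from 50,000/uL up to the Grade 1 boundary undecided

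*Combined protocol and SAP*

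**What the plan says.** Table 1 (Section 9.2.3) opens its platelet row with the hold trigger, "Thrombocytopenia: Platelets < 35,000 /uL". The standard restart condition is resolution to less than "Grade 2 (50,000/uL, may restart at next lower dose level". The bracket opens before the number and closes only after the restart action, and no comparator stands in front of 50,000.

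A separate bullet in the same row covers subjects in whom benefit is seen: those who "recover to at least 40,000/uL platelets, may be considered for retreatment with a dose reduction after consultation with the study PI", case by case.

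The neutropenia, Grade 4 anemia and related Grade 3 non-hematologic rows all set restart at Grade 2 or better (≤ Grade 2). Only the platelet row uses a strict less-than sign.

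On long holds, the text of Section 9.2.3 says: "Subjects with hematologic toxicities requiring dose holds for 3 weeks or longer will be removed from the study". The note under Table 1 repeats this rule and adds that the study PI may permit otherwise in individual cases.

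The grading scale is adopted by reference in Appendix 3: "Adverse Events will be graded according to the National Cancer Institute Common Toxicity Criteria for Adverse Events (CTCAE), Version 4". The platelet cut-offs for each grade are not reproduced.

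The caption of Table 2 reads "Optional Dose Increase or Mandatory Reduction Levels for Subjects initiating treatment at 15 mg daily", and that of Table 3 ends "Levels for Subjects initiating treatment at 10 mg daily". Section 9.2.1 says that subjects in the higher platelet stratum "will begin dosing at 15 mg BID (three 5 mg tablets BID", and every row in both tables says BID.

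**The concern.** A restart rule should give one answer for one platelet count. Here the grade and the number can give different answers, and nothing in the row says which governs. Section 3.3 names thrombocytopenia as the dose-limiting toxicity in the myelofibrosis study, so the line is likely to be used.

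The study has four sites. If one follows the number and another the grade, two subjects with the same count can differ in hold length. A hold that lasts longer only because of the reading may reach 3 weeks and raise the question of removal. Exposure, and possibly time on study, would then depend partly on how a site reads one line.

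**Working it through.** The plan states no figure to reproduce here. The check sets the provisions side by side.

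**Inputs**

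| Provision | Platelets | Comparison |
|---|---|---|
| Hold trigger, Table 1 | < 35,000/uL | Neutropenia hold: Grade 3 or 4, ANC < 1000/uL |
| Standard restart, Table 1 | less than Grade 2, with 50,000/uL bracketed | Other three restart rows: ≤ Grade 2 |
| Exception for subjects with benefit, Table 1 | ≥ 40,000/uL | Neutropenia exception: recovery to at least Grade 3 |
| At least weekly counts, Section 9.2.3 | < 50,000/uL | ANC < 1000/uL |
| Entry, Section 6.1 | ≥ 75,000/uL | |

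**Step 1: where 50,000/uL sits on the grade scale.** Section 9.2.3 pairs platelets < 50,000/uL with ANC < 1000/uL. Table 1 labels ANC < 1000/uL as Grade 3 or 4. If the pairing follows the grades, 50,000/uL divides Grade 2 from Grade 3 and is the lower edge of Grade 2. The exceptions fit this: in the neutropenia row the standard level is ≤ Grade 2 and the exception reaches down to Grade 3; in the platelet row the number is 50,000/uL and the exception reaches down to 40,000/uL. So 50,000/uL occupies the place that ≤ Grade 2 holds in the neutropenia row.

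**Step 2: what the sign requires.** Less than Grade 2 means Grade 1 or better. Let X be the count at which Grade 2 ends and Grade 1 begins. The grade reading requires a count of at least X. The number, read as a minimum, requires at least 50,000/uL.

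**Step 3: the disputed range.** The two readings differ for counts from 50,000/uL to below X, a width of X − 50,000.

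- X = 50,000/uL: width 0, so grade and number agree.
- X = 75,000/uL (assumption): 75,000 − 50,000 = 25,000/uL, so the range is 50,000 to below 75,000/uL.

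**Step 4: an example under X = 75,000/uL.** A held subject recovers to 60,000/uL. By the number, 60,000 ≥ 50,000 and restart at the next lower dose level is allowed. By the grade, 60,000 < 75,000 and the hold continues. A subject who entered at the minimum of 75,000/uL would have to regain the full entry count.

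**Step 5: the captions.** Taken literally, they imply 15 or 10 mg per day. The rows and Section 9.2.1 give 2 × 15 = 30 mg or 2 × 10 = 20 mg per day. No row or dosing instruction carries the once-daily figure.

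**The case against.** The line prints one platelet number and one grade. A reader might infer that it prints two different platelet levels. It does not: the second level depends on a cut-off that the documents cite but do not give. The pairing in Section 9.2.3 concerns how often counts are taken, not grading, so it suggests a mismatch without proving one. Sites may well treat 50,000/uL as the working threshold, since Section 9.2.2 also uses it. The less-than sign could be a slip for less-than-or-equal, although the other rows print that sign correctly. All of this stands, and it limits the point to an apparent mismatch. It does not tell a site which half of the line governs.

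The 40,000/uL bullet is a conditional exception and does not contradict the standard criterion. It also softens the example: a subject at 60,000/uL in whom benefit is seen could be considered for retreatment on either reading, after consulting the PI. The conflict therefore matters most for subjects outside that exception.

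Three stronger inferences are tempting, and the documents do not support them:

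- **That the reading decides who is removed and becomes a non-responder.** The note under Table 1 gives the PI discretion over the 3-week rule. Nothing in Sections 12.1 or 12.2.1 makes a removed subject a non-responder; one with a response already documented could still count as a responder.
- **That about a quarter of subjects are affected.** Section 3.1 reports Grade 3 or 4 platelet declines in 40 of 154 myelofibrosis subjects (40/154 = 26%). That is a different disease, with a median of about 15 months on drug. The figure measures neither holds below 35,000/uL nor recoveries into the disputed range.
- **That Tables 2 and 3 create a two-fold dosing difference.** Only the captions lack BID; the starting-dose rows have it, as do Sections 3.4, 9.1.1 and 9.2.1.

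**Conclusion.** The point holds as an internal inconsistency in one safety criterion. The grade and the number in the platelet restart line appear not to match, and the row does not say which governs. The evidence is the pairing in Section 9.2.3 and the different sign in the other three restart rows.

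The size depends on the Grade 1 boundary. The disputed range runs from 50,000/uL to below 75,000/uL if that boundary is 75,000/uL, and vanishes if it is 50,000/uL. The number of subjects who would fall in the range cannot be derived from the documents. The consequence is a possibly longer hold, which may reach the 3-week rule subject to the PI's exception, and possible variation between sites.

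The captions of Tables 2 and 3 are a clerical matter and carry no weight in this conclusion.

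**What to change.** The sponsor and investigator should reconcile the grade and the number in the platelet row of Table 1 into one unambiguous restart criterion, with an explicit comparator and a correctly closed bracket. If the criterion keeps a grade, the corresponding count should be printed beside it so that sites need not look it up. Which level applies is for the sponsor and investigator to decide. As an editorial correction, the captions of Tables 2 and 3 should be reconciled with their rows and with Section 9.2.1.

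The cost is wording in three tables at the next amendment and a notice to the four sites. No procedure, visit or sample size changes.
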